16.1 Sample size calculation

We aim at recruiting between 100-200 clinicians within the 10 month time period of recruitment (August 2020-April 2021). This will be sufficient to address the objectives of the study. We will stop recruiting and close down the website when we have accrued 300 respondents with complete data within the recruitment period (before April 2021).

We want to compare the means of the weighting of advice (WOA) of the two groups, (the group receiving advice labelled as coming from an algorithm and the group receiving advice labelled as coming from a clinician), with a confidence interval (CI) of 95%. Based on calculations from a similar study by Logg et al. (2019) we expect the standard deviation (SD) to be between 0.3 and 0.4. This will give a width of the CI between 0.17 and 0.31, depending on the sample size and the SD (see the table below). These numbers are based on and calculated from the guidelines by Machin et al. (2018). This means that a sample size between 100-200 respondents should be sufficient to detect a significant difference between the mean WOAs of the two groups if the mean difference is greater than 0.085 to 0.22.

Table 1: The width of the confidence interval varying by sample size and SDs

Sample Size	Expected SD for mean diff in WOA	
	$\sigma = 0.3$	$\sigma = 0.4$
50	0.33	0.44
100	0.24	0.31
150	0.19	0.26
200	0.17	0.22
250	0.15	0.20
300	0.14	0.18

The calculations above are sufficient to address the primary objective of the study which is to assess the level to which clinicians incorporate advice received from other clinicians or an algorithm into their estimates of the prognosis of palliative care patients.

The online survey consists of five vignettes. Increasing the number of vignettes would increase generalisability of the study but would add to the study burden for the participants and increase the risk that the study would not be completed by respondents. It was considered that five vignettes was a suitable balance between generalisability and study burden.

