4.3 Analysis of the primary objective

In order to assess the level to which participants incorporate the advice into their final estimates of the probability of survival, the WOA is calculated for each participant for each vignette(s). This is done by comparing their final estimate against the initial estimate and the advice provided. The final

estimate of probability of surviving two weeks can be represented as a weighted combination of the participant's initial estimate and the advice received, with the weights being proportional to the extent of the shift towards (away from) the advice. WOA will be defined as $= |f - i|/|a - i|$, where 'i', 'f', and 'a' stand for initial, final, and advice, respectively.

If a participant decides to adhere completely to his or her initial estimate (100% discounting of the advice), the weight of the advice will be 0. If the participant decides to shift completely to the advice then the weight of advice will be 1.0 (0% discounting). Intermediate weights indicate that positive weights were assigned to the initial estimate and the advice (partial discounting).

We will then use multilevel regression analysis accounting for multiple vignettes completed by each participant, to compare the means of the WOA scores for the two arms, the algorithm arm and the clinicians' arm.

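### The stated detectable difference of 0.085 to 0.22 does not follow from Table 1, whose half-widths for 100–200 respondents run from 0.085 to 0.155

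*Protocol*

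**What the plan says.** Protocol section 16.1 sizes the study on the precision of the difference in mean WOA between the algorithm and clinician groups, using a 95% confidence interval. On the SD it says "we expect the standard deviation (SD) to be between 0.3 and 0.4". For 100–200 respondents it then says "This will give a width of the CI between 0.17 and 0.31, depending on the sample size and the SD", and Table 1 lists widths for totals of 50 to 300 at the two SDs, under the column heading "Expected SD for mean diff in WOA".

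From these widths it concludes that 100–200 respondents are "sufficient to detect a significant difference between the mean WOAs of the two groups if the mean difference is greater than 0.085 to 0.22". After the table it adds: "The calculations above are sufficient to address the primary objective of the study".

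No power is stated. The SAP has no sample size section, so it neither repeats nor corrects the figure. SAP section 4.3 sets out the primary comparison: "We will then use multilevel regression analysis accounting for multiple vignettes completed by each participant".

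**The concern.** The protocol offers the detectable difference as following from the widths. If the link is the usual one, that a 95% interval excludes zero when the observed difference exceeds half its width, the range should be half of 0.17 to half of 0.31. The lower end fits this and the upper end does not.

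This is the only detectable difference in either document, and the protocol relies on the calculation when it calls the study adequate for its primary objective. A reader judging a null or borderline result would look here. As written, the reader cannot tell whether the figures are significance thresholds for an observed difference or true differences the study would probably detect. Neither reading makes both ends right.

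**Working it through.** **Inputs (all from Protocol section 16.1 unless noted).** Two-sided 95% interval; SD 0.3 to 0.4; total N of 100 to 200. The allocation ratio is not stated. I assume 1:1, so N/2 per group.

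**Step 1: reproduce Table 1.** Full width = 2 × 1.96 × SD × √(4/N).

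| N | SD 0.3: computed (table) | SD 0.4: computed (table) |
|---|---|---|
| 50 | 0.333 (0.33) | 0.443 (0.44) |
| 100 | 0.235 (0.24) | 0.314 (0.31) |
| 150 | 0.192 (0.19) | 0.256 (0.26) |
| 200 | 0.166 (0.17) | 0.222 (0.22) |
| 250 | 0.149 (0.15) | 0.198 (0.20) |
| 300 | 0.136 (0.14) | 0.181 (0.18) |

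All 12 cells match. The entries are therefore full widths, N is the total, allocation is 1:1, and each participant contributes one WOA value with within-group SD 0.3 or 0.4.

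**Step 2: half-widths for N = 100–200.**

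- From the rounded table: 0.17/2 = 0.085 and 0.31/2 = 0.155.
- Unrounded: 0.083 (N=200, SD 0.3), 0.111 (N=200, SD 0.4), 0.118 (N=100, SD 0.3) and 0.157 (N=100, SD 0.4).

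The lower stated figure reproduces. The upper one does not.

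**Step 3: look for a basis that gives 0.22.** It is the half-width at N=50, SD 0.4 (0.222), which is outside the stated range. It is also the full width at N=200, SD 0.4 (0.222), and close to the 80%-power difference at N=100, SD 0.4 (0.224). The documents do not say which was meant.

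**Step 4: test whether any single criterion gives both ends.** Each candidate is a constant × SD/√N, apart from negligible t corrections. The ratio of its largest to smallest value is therefore (0.4/0.3) × √(200/100) = 1.89. The stated ratio is 0.22/0.085 = 2.59, or at least 0.215/0.0855 = 2.51 allowing for rounding. Specific versions agree that nothing fits:

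| Criterion | Range |
|---|---|
| Half-width, t-based | 0.084–0.159 |
| Half-width, N per group | 0.059–0.111 |
| Half-width, 99% interval | 0.109–0.206 |
| 80% power | 0.119–0.224 |
| 90% power | 0.138–0.259 |

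Averaging five vignettes multiplies both ends by the same factor at any fixed intraclass correlation (ICC), so it leaves the ratio unchanged.

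**Step 5: the power reading, one WOA per participant.** Power at a true difference of 0.085 (noncentral t, N − 2 degrees of freedom) is:

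| | SD 0.3 | SD 0.4 |
|---|---|---|
| N=200 | 51% | 32% |
| N=100 | 29% | 18% |

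The 80%-power difference is (1.96 + 0.842) × SD × √(4/N). This is 0.119 at N=200, SD 0.3 and 0.224 at N=100, SD 0.4.

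**Step 6: how far the SD basis matters.** Read literally, the Table 1 heading makes 0.3–0.4 the SD of the mean difference. The width would then be 2 × 1.96 × 0.3 = 1.18 whatever N, so the heading cannot be right. If 0.3–0.4 is instead the SD of a single vignette's WOA and five are averaged, the effective SD is multiplied by √((1 + 4 × ICC)/5). The documents give no ICC, so the values below are assumptions.

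| Assumed ICC | Factor | Power at 0.085, N=200: SD 0.3 / SD 0.4 | Half-widths | 80%-power differences |
|---|---|---|---|---|
| 0.2 | 0.600 | 91% / 70% | 0.050–0.094 | 0.07–0.13 |
| 0.5 | 0.775 | 73% / 49% | 0.064–0.121 | 0.09–0.17 |
| 0.8 | 0.917 | 59% / 37% | 0.076–0.144 | 0.11–0.21 |

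**The case against.** The strongest reply is that this is one wrong number in one sentence. The study is sized on interval width, a legitimate choice, and the widths are right. As a significance threshold 0.22 errs on the cautious side, so precision is not overstated. Table 1 follows directly and lets a reader recover 0.155. No recruitment or stopping rule uses 0.22, and the SAP calls the analysis mainly descriptive. On the protocol's own logic 0.085 is a correct half-width, and about 50% power at a half-width is true of any study. An 80% target appears nowhere in the documents. If the SD is per vignette, power at 0.085 could be as high as 91%.

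Much of this stands. It limits the consequences and shows that the power figures depend on how the sentence is read. It does not rescue the range, because no reading gives both ends. The power reading is also not far-fetched, since the protocol speaks of a sample size being enough to detect a difference. Changing 0.22 to 0.155 alone would mend the arithmetic but leave a claim that can be taken for power when, at the half-width, power is about 50%. The per-vignette results show why the SD basis should be stated. They do not defend the sentence.

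**Conclusion.** The concern holds. For 100–200 respondents the half-widths are 0.085 to 0.155 from the rounded table (0.083 to 0.157 unrounded), so the stated upper end of 0.22 is wrong as a half-width. On Table 1's basis the 80%-power range is 0.12 to 0.22, so the lower end of 0.085 is wrong as a powered difference.

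The mismatch itself needs only the protocol's own figures. The recalculated values assume 1:1 allocation, which every Table 1 cell supports. The power figures also assume one WOA value per participant, and the per-vignette alternatives rest on assumed ICCs.

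Table 1 and the 0.17 to 0.31 range are correct. The sentence should be corrected because it is the study's only sensitivity statement, but no analysis or recruitment target changes.

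**What to change.** Replace the sentence in Protocol section 16.1 with wording such as: *Assuming one WOA value per participant with SD 0.3 to 0.4 and equal allocation, 100–200 analysed participants give a 95% CI half-width of 0.08 (N=200, SD 0.3) to 0.16 (N=100, SD 0.4). True differences of 0.12 to 0.22, respectively, would be detected with 80% power at the two-sided 5% level.* The half-widths are the unrounded 0.083 and 0.157 to two decimals. If the authors prefer to claim precision only, the first sentence is enough, provided the language of detection is dropped.

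State whether the SD is per vignette or per participant mean and, if per vignette, the assumed ICC. Correct the Table 1 heading to match. Optionally add the half-widths at the cap of 300 respondents, which are 0.07 (SD 0.3) and 0.09 (SD 0.4).

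The cost is one sentence and one table heading, with no extra participants and no change to the SAP's model. The upper threshold for significance becomes more favourable (0.16 instead of 0.22). If a power claim is kept, its lower end becomes less favourable (0.12 instead of 0.085).

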16.2 Statistical analysis

A fully detailed statistical analysis plan will be drawn up in a separate document prior to data analysis. Participants who do not complete the required number of vignettes or violate the protocol (e.g. providing the same estimate for every vignette) will be removed from the analysis.

16.2.1 *Summary of baseline data and flow of participants*

Baseline demographic characteristics (gender, age, work environment, role, seniority, expertise) will be summarised by group and overall. As a result of the randomisation process, we expect them to be balanced across groups. Categorical data will be described using numbers and percentages. Continuous data will either be described with mean and standard deviation, or median and interquartile range, pending the distribution. We will produce a CONSORT flow diagram of all participants (<http://www.consort-statement.org/>).

16.2.2 *Primary outcome analysis*

The primary outcome will be clinicians' estimates of the probability of a patient surviving for two weeks. In order to assess the level to which participants incorporate the advice into their final estimates of the probability of survival, the WOA is calculated for each participant for each vignette(s). This is done by comparing their final estimate against the initial estimate and the advice provided. The final estimate of probability of surviving two weeks can be represented as a weighted combination of the participant's initial estimate and the advice received, with the weights being proportional to the extent of the shift towards (away from) the advice. WOA will be defined as $= |f - i|/|a - i|$, where 'i', 'f', and 'a' stand for initial, final, and advice, respectively (Yaniv, 2004a).

If a participant decides to adhere completely to his or her initial estimate (100% discounting of the advice), the weight of the advice will be 0. If the participant decides to shift completely to the advice then the weight of advice will be 1.0 (0% discounting). Intermediate weights indicate that positive weights were assigned to the initial estimate and the advice (partial discounting) (Yaniv and Kleinberger, 2000a).

We will then use regression analyses to compare the means of the WOA scores for the two arms, the algorithm arm and the clinicians' arm.

16.2.3 *Secondary outcome analysis*

The secondary outcome will be clinicians' estimates of the probability of a patient surviving for two weeks. We will perform regression analyses to explore any associations between participants' weighting policies and characteristics of the participants (gender, age, work environment, role, seniority, expertise, confidence).

We want to explore any associations between participants' weighting policies and the advice itself (e.g. the strength of the advice) as well. Participants will receive five pieces of advice from the PiPS data. They will receive advice given with high confidence from 85% and upwards (i.e. the patient has 90% probability of surviving the next 14 days), with lower confidence (i.e. 75% probability of survival) and one where the advice is equivocal (i.e. 50% probability of survival). Multilevel regression analyses will be used to take into account multiple vignettes are completed by each participant.

17 Record keeping and archiving

At the end of the study, all essential documentation will be archived securely by the CI for a minimum of 20 years from the declaration of end of study.

Essential documents are those which enable both the conduct of the study and the quality of the data produced to be evaluated and show whether the site complied with all applicable regulatory requirements.

The sponsor will notify the research team when study documentation can be archived. All archived documents must continue to be available for inspection by appropriate authorities upon request.

18 Study Management Group (SMG)

The SMG will be formed of the CI ([name]) and all of the personnel listed in section 1. The group will meet regularly and will review recruitment figures and substantial amendments to the protocol prior to submission to the REC.

19 Ethics

The sponsor will ensure that the study protocol, PIS, consent form and submitted supporting documents have been approved by the appropriate Research Ethics Committee, prior to any participant recruitment. The protocol, all other supporting documents including and agreed amendments, will be documented and submitted for ethical and regulatory approval as required. Amendments will not be implemented prior to receipt of the required approval(s).

An annual progress report (APR) will be submitted to the REC within 30 days of the anniversary date on which the favourable opinion was given, and annually until the study is declared ended. The CI or delegate will prepare the APR.

Within 90 days after the end of the study, the CI/Sponsor will ensure that the main REC is notified that the study has finished. If the study is terminated prematurely, those reports will be made within 15 days after the end of the study.

The CI or delegate will supply the Sponsor with a summary report of the study, which will then be submitted to the REC within 1 year after the end of the study.

20 Patient and public involvement (PPI)

This study does not involve patients or members of the public directly. The participants are all clinicians working in palliative care. The CI ([name]) is a Palliative Care Consultant and a member of the Study Management Group. As such, he has been involved in the design of the research and will be involved in management of the research, undertaking the research, analysis of results and dissemination of findings. In addition, we will ask a small number of other palliative care clinicians to review the recruitment materials and pilot the study website.

21 Monitoring

The sponsor will determine the appropriate level and nature of monitoring required for the study. Risk will be assessed on an ongoing basis and adjustments made accordingly.

The degree of monitoring will be proportionate to the risks associated with the study.

22 Finance

This study is funded by the Marie Curie Chair's grant and the Marie Curie I-CAN-CARE Programme grant (MCCC-FPO-16-U). There are no financial interests by the CI, PI, or study management members.

23 Insurance

University College London holds insurance against claims from participants for injury caused by their participation in the study. Participants may be able to claim compensation if they can prove that UCL has been negligent.

Participants may also be able to claim compensation for injury caused by participation in this study without the need to prove negligence on the part of University College London or another party. Participants who sustain injury and wish to make a claim for compensation should do so in writing in the first instance to the Chief Investigator, who will pass the claim to the Sponsor's Insurers, via the Sponsor's office.

24 Publication policy

60%	Reduced	Unable hobby/house work Significant disease	Occasional assistance necessary	Normal or reduced	Full or Confusion
50%	Mainly Sit/Lie	Unable to do any work Extensive disease	Considerable assistance required	Normal or reduced	Full or Confusion
40%	Mainly in Bed	Unable to do most activity Extensive disease	Mainly assistance	Normal or reduced	Full or Drowsy +/- Confusion
30%	Totally Bed Bound	Unable to do any activity Extensive disease	Total Care	Normal or reduced	Full or Drowsy +/- Confusion
20%	Totally Bed Bound	Unable to do any activity Extensive disease	Total Care	Minimal to sips	Full or Drowsy +/- Confusion
10%	Totally Bed Bound	Unable to do any activity Extensive disease	Total Care	Mouth care only	Drowsy or Coma +/- Confusion
0%	Death	-	-	-	-

What do you think the probability is that this patient will survive the next two weeks?

.....%

Please write your answer as a percentage in the box to the right

(Scale: 0-100. Where 0% means certain to die and 100% means certain to survive)

FOR THE CLINICIAN ADVICE:

A palliative care [nurse/doctor] estimated (based on the provided patient information) that the probability this patient will survive the next two weeks was:

.....%

FOR THE ALGORITHM ADVICE:

The PiPS-B14 estimated (based on the provided patient information) that the probability this patient will survive the next two weeks was:

.....%

What is your final estimate of the probability this patient will survive the next two weeks?

.....%

Study of Advice and Decision-making on prognosis using the Judge-advisor System within multi-disciplinary Teams (ADJUST)

– Statistical Analysis Plan (version 1.0 26.03.2021)

1 Study Summary

For full details see the study protocol (version 1.0 01.09.2020).

Title	Study of Advice and Decision-making on prognosis using the Judge-advisor System within multi-disciplinary Teams (ADJUST)
Short title	ADJUST: A study on MDT prognostication
Lead Investigators	[name] and [name]
Statistician	[name]
Design	Online psychological experiment
Objectives	To understand how clinicians form intuitive judgements about the prognoses of palliative care patients after receiving advice perceived as coming from either a team member or an algorithm. Primary objective: To assess the level to which clinicians incorporate advice received from other clinicians or an algorithm into their estimates of the prognosis of palliative care patients. Secondary objective: To investigate the extent to which clinicians' integration of advice is influenced by the characteristics of the judge, the advisor or the advice itself.
Population	100-300 palliative care clinicians
Registration	Clinicaltrials.gov NCT04568629 (29/09/2020). Prospectively registered

2 Introduction

2.1 Purpose and scope of the statistical analysis plan

This document describes the main statistical analyses to be applied to the data from the ADJUST study. This Statistical Analysis Plan was written by [name] in collaboration with [name], [name], and [name].

2.2 Timing of Analysis

The analysis will be performed after all the data have been checked and locked and the analysis plan has been finalised. When checking the data we will remove participants who have violated the protocol (e.g. putting the same answer for every vignette).

3 Data collection

3.1 Participant characteristics

The following demographic data will be collected from all participants recruited into the study:

1. Profession
2. Age
3. Gender
4. Work environment (hospice, hospital, community service)
5. Country of employment
6. Professional level
7. Years of experience
8. Years of palliative care experience

3.2 Outcome data

Each participant will be asked to complete five vignettes. The primary and secondary outcomes will be provided for all vignettes.

3.2.1 Primary outcome measures

The primary outcome will be clinicians' continuous estimates of the probability of a patient surviving for two weeks (measured from 0% 'certain to die' to 100% 'certain survival'). Participants provide an initial and a final estimate of the probability of survival.

3.2.2 Secondary outcome measures

The secondary outcome will be clinicians' estimates of the probability of a patient surviving for two weeks and the characteristics of the participants (profession, gender, age, work environment etc.).

4 Statistical analysis plan

Data analysis will be mainly descriptive and focused on addressing the overall objective "To understand how clinicians form intuitive judgements about the prognoses of palliative care patients after receiving advice perceived as coming from either a team member or an algorithm".

4.1 Analysis of participant demographics

Summary measures for the characteristics of participants will be presented using means (with standard deviations), medians (with interquartile ranges), counts and proportions, as appropriate. The number of missing observations for each characteristic will be reported.

4.2 Missing data

Participants who do not complete the five vignettes will be removed from the analysis.

We will report the number of vignettes each participant completed. Potential bias due to missing data will be investigated by comparing characteristics of those who completed sufficient vignettes with those who did not complete sufficient vignettes.

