Clinicians will be invited to participate in the study as part of a (online) seminar on palliative care by the CI or through an invitation email sent to their hospice medical director (see section 12.3). Seminar participants will receive information about the study before the seminar and will be invited to complete the online questionnaire in preparation for the seminar. The CI will make it clear that delegates at the seminar are under no obligation to complete the questionnaire.

Participants will be provided with a link to the study website and will complete all assessments online. The website will provide information regarding the study and a link to a PIS. Participants will be asked to tick check boxes to indicate that they are giving informed consent. After filling in the demographics section, eligible participants will be considered to be enrolled and a participant ID will be assigned. Next, participants will be randomly allocated to one of the two study groups. This will be performed through the web-based system, using a pre-generated blocked randomisation list.

Participants will be given tailored instructions, shown a practice vignette and will then be able to start the decision tasks and to provide estimates of the probability of patients surviving two weeks. Participants will be presented with five vignettes. Vignettes will be presented in random order to prevent order effects.

There will be no time limit for completion, so that each participant will be able to consider their responses. Participants will be given the opportunity to log out and return to the same place at a more convenient time. Participants will not be able to move on to the next page if required information is missing or is in an incorrect format (e.g. incorrect email format). The online environment will be piloted by the study team in close collaboration with the study statistician who will review the data being collected before, during, and at the start of the recruitment phase to ensure data integrity.

After completing the series of vignettes, participants will be shown a debrief page to remind the participant what the results will be used for and they will be able to download a certificate of participation. Participants will be asked if they wish to receive a summary of the results at the end of the study and whether they would be willing to be approached for subsequent studies.

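### Randomised participants who complete one to four of the five vignettes are removed, although the planned multilevel model can use their data

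*SAP*

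**What the plan says.** SAP 4.2: "Participants who do not complete the five vignettes will be removed from the analysis". Protocol 16.2 agrees: "Participants who do not complete the required number of vignettes or violate the protocol (e.g. providing the same estimate for every vignette) will be removed". Neither document gives a reason for the rule, and neither plans an analysis that keeps the partial records.

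The order of events is in Protocol 11. Participants complete the demographics and are enrolled. "Next, participants will be randomly allocated to one of the two study groups". The practice vignette and the five study vignettes follow. On order, the protocol says "Vignettes will be presented in random order to prevent order effects".

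SAP 4.3 calculates WOA for each participant and vignette, and compares the two label groups by "multilevel regression analysis accounting for multiple vignettes completed by each participant".

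The plan expects some people not to finish. Protocol 16.1 explains that more vignettes "would add to the study burden for the participants and increase the risk that the study would not be completed by respondents". Protocol 11 adds: "Participants will be given the opportunity to log out and return to the same place at a more convenient time". Protocol 14.1 provides one reminder email, in Arm B only. SAP 4.2 reports the number of vignettes completed and compares the characteristics of participants with and without sufficient vignettes.

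**The concern.** Everyone removed under this rule has already been randomised. Anyone who has finished at least one vignette has also seen the labelled advice, which is the experimental manipulation, and has given an initial and a final estimate. Their WOA for that vignette can be calculated unless the initial estimate equals the advice.

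Two things are at stake. The first is precision: usable randomised data are thrown away. The second is bias: the decision to stop comes after exposure to the label, so the completers in the two groups need not be comparable. If stopping were related to WOA in one group and not in the other, the completers-only difference would be too small or too large. Comparing the characteristics of completers and non-completers might hint at this but would not correct the estimate.

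**Working it through.** **The plan's own figure.** Protocol 16.1, Table 1, gives the full width of the 95% CI for the difference in mean WOA. With 1:1 allocation and one value per participant, width = 2 × 1.96 × SD × 2/√N. For N = 100 this gives 0.235 (SD 0.3) and 0.314 (SD 0.4), against 0.24 and 0.31 in the table. For N = 200 it gives 0.166 and 0.222, against 0.17 and 0.22. All 12 cells agree to two decimals. The table makes no allowance for dropout.

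**Information in a partial record.** Dropout and ICC are assumed from here on. A participant with k vignettes contributes information proportional to 1/[ICC + (1 − ICC)/k]. Relative to a completer this is [ICC + (1 − ICC)/5] / [ICC + (1 − ICC)/k]. For k = 2 and ICC 0.4: 0.52/0.70 = 0.74.

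| Vignettes completed | ICC 0.2 | ICC 0.4 | ICC 0.6 |
|---|---|---|---|
| 1 | 36% | 52% | 68% |
| 2 | 60% | 74% | 85% |
| 4 | 90% | 95% | 97% |

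**Effect on the CI.** If a share d stops early, each with relative information r, the ratio of the completers-only width to the all-vignettes width is √[(1 − d + d·r)/(1 − d)]. For d = 0.10 and r = 0.74: √(0.974/0.90) = 1.040. For stopping after two or three vignettes and ICC 0.2 to 0.6:

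- 5% dropout: about 2% wider
- 10% dropout: 3–5% wider
- 20% dropout: 7–11% wider

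**Bias.** Assumptions: N = 200 in two equal groups, true difference 0.10, SD 0.35 for participant means, ICC 0.4, stopping after the second vignette. The CI half-width without dropout is 1.96 × 0.35 × 2/√200 = 0.097. In one group the chance of stopping differs according to whether the mean WOA of the first two vignettes is below or above the group mean; in the other group it is constant. The completers' mean in the linked group then shifts by

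[(p_low − p_high)/2] / (share retained) × 0.798 × SD × 0.52/√0.70,

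where SD is per vignette, 0.35/√0.52 = 0.485. For 40%/10% stopping: (0.15/0.75) × 0.798 × 0.485 × 0.622 = 0.048.

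A simulation (8,000 replicates per scenario, Monte Carlo SE 0.0006) compared the completers' mean difference with a random-intercept analysis of all vignettes. Each pair is the estimate with the link in the lower-WOA group, then in the higher-WOA group.

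| Stopping, low/high WOA in one group v other group | Completers only | All vignettes, stopping depends on observed WOA | Completers only, stopping depends on unseen WOA | All vignettes, stopping depends on unseen WOA |
|---|---|---|---|---|
| 12%/8% v 10% | 0.094 / 0.106 | 0.099–0.101 | 0.095 / 0.106 | 0.098 / 0.102 |
| 15%/5% v 10% | 0.087 / 0.114 | 0.099–0.101 | 0.085 / 0.113 | 0.094 / 0.105 |
| 30%/10% v 20% | 0.070 / 0.130 | 0.099–0.101 | 0.068 / 0.133 | 0.089 / 0.112 |
| 40%/10% v 15% | 0.052 / 0.147 | 0.099–0.101 | 0.048 / 0.151 | 0.082 / 0.118 |

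The first completers-only column is for stopping that depends on observed WOA. Completers-only gave 0.10 when stopping was unrelated to WOA, even with different dropout rates (15% v 25%), and when it was equally related in both groups.

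With WOA bounded at 0 and 1 (per-vignette SD 0.34) and observed-WOA stopping, the completers-only errors in the four rows were 0.004, 0.010, 0.021 and 0.034. The all-vignettes errors were at most 0.001.

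**The case against.** The strongest case against runs as follows.

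- **The bias is hypothetical.** No document shows a link between stopping and WOA, let alone one confined to a single label group. This stands. The two larger scenarios need 15–25% dropout and a strong one-sided link.
- **The assumed SD is high.** An SD of 0.35 for participant means at ICC 0.4 implies 0.485 per vignette, whereas Protocol 16.1 expects 0.3 to 0.4 without saying which it means. If 0.35 is the per-vignette SD, the largest shift falls from 0.048 to 0.035. The half-width falls too, to 1.96 × 0.35 × √0.52 × 2/√200 = 0.070, so the bias is still about half of it. The objection changes the absolute scale, not the relative importance.
- **The loss may be small and partly made up.** The task takes 10 to 15 minutes, participants can return later, and Protocol 16.1 says "We will stop recruiting and close down the website when we have accrued 300 respondents with complete data", so recruitment can replace partial completers. This stands in part. However, 300 is an upper stop while the stated aim is 100–200, and replacement does nothing for bias.
- **Partial records weaken other safeguards.** The same-answer check cannot be applied to a single vignette and is weak with two. The vignette mix is also no longer balanced by design. The first is a real but small cost, which a completers-only sensitivity analysis covers. On the second, random order makes the imbalance a matter of chance. With vignette effects added, the all-vignettes estimate remained unbiased and more precise than completers-only.
- **The plan already describes the loss.** A CONSORT diagram, counts of vignettes completed and a comparison of characteristics are planned, and SAP 4 calls the analysis mainly descriptive. These points lower the weight of the concern, but none of them returns data to the analysis or corrects an estimate.

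**Conclusion.** The concern holds. It is a change that should be made, not a flaw that invalidates the study. The certain part is the avoidable loss of randomised data from anyone who stops after one to four vignettes. It costs a few per cent of CI width at 5–10% dropout and 7–11% at 20%, for ICC 0.2 to 0.6 and stopping after two or three vignettes. The bias is conditional on an undocumented link: negligible if stopping is unrelated to WOA or equally related in both groups, and up to about half the CI half-width in the most extreme scenario examined. Using all vignettes removes that bias when stopping depends on observed WOA, and reduces it without removing it when stopping depends on vignettes never seen. Dropout, ICC and the stopping mechanism are all assumptions, because the documents give none of them.

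**What to change.** In SAP 4.2 and Protocol 16.2, define the primary analysis population as all randomised participants with at least one calculable WOA (initial and final estimate given, and initial estimate different from the advice). Analyse them in the group allocated, using every completed vignette in the multilevel model already planned. Keep the completers-only analysis as a sensitivity analysis. Report vignettes completed and all removals by randomised group, and say how the same-answer rule applies to short records.

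The cost is wording in these two sections. The partial records must already be held, because SAP 4.2 plans to report how many vignettes each participant completed. The downside is that a few low-effort partial responders may enter the primary analysis; the sensitivity analysis shows whether that matters. The change cannot recover participants who leave before giving any WOA, and it still assumes that stopping depends on observed data and that the model is reasonable.
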